8.1.4.1. Reporting SAEs to Pfizer Safety

All SAEs occurring in a subject during the active collection period are reported to Pfizer Safety on the CT SAE Report Form.

SAEs occurring in a subject after the active collection period has ended are reported to Pfizer Safety if the investigator becomes aware of them; at a minimum, all SAEs that the investigator believes have at least a reasonable possibility of being related to investigational product must be reported to Pfizer Safety.

Follow up by the investigator continues throughout and after the active collection period and until the event or its sequelae resolve or stabilize at a level acceptable to the investigator, and Pfizer concurs with that assessment.

8.1.4.2. Recording Non-serious AEs and SAEs on the CRF

During the active collection period, both non-serious AEs and SAEs are recorded on the CRF.

Follow-up by the investigator may be required until the event or its sequelae resolve or stabilize at a level acceptable to the investigator, and Pfizer concurs with that assessment.

8.1.5. Causality Assessment

The investigator's assessment of causality must be provided for all AEs (serious and non-serious); the investigator must record the causal relationship on the CRF, and report such an assessment in accordance with the SAE reporting requirements, if applicable. An investigator's causality assessment is the determination of whether there exists a reasonable possibility that the investigational product caused or contributed to an AE; generally the facts (evidence) or arguments to suggest a causal relationship should be provided. If the investigator does not know whether or not the investigational product caused the event, then the event will be handled as "related to investigational product" for reporting purposes, as defined by the sponsor. If the investigator's causality assessment is "unknown but not related" to investigational product, this should be clearly documented on study records.

In addition, if the investigator determines that an SAE is associated with study procedures, the investigator must record this causal relationship in the source documents and CRF, and report such an assessment in the dedicated section of the CT SAE Report Form and in accordance with the SAE reporting requirements.

8.1.6. Sponsor's Reporting Requirements to Regulatory Authorities

AE reporting, including suspected unexpected serious adverse reactions, will be carried out in accordance with applicable local regulations.

8.2. Definitions

8.2.1. Adverse Events

An AE is any untoward medical occurrence in a study subject administered a product or medical device; the event need not necessarily have a causal relationship with the treatment or usage. Examples of AEs include, but are not limited to:

- Abnormal test findings;
- Clinically significant signs and symptoms;
- Changes in physical examination findings;
- Hypersensitivity;

- Progression/worsening of underlying disease;
- Drug abuse;
- Drug dependency.

Additionally, AEs may include signs and symptoms resulting from:

- Drug overdose;
- Drug withdrawal;
- Drug misuse;
- Drug interactions;
- Extravasation;
- Exposure during pregnancy (EDP);
- Exposure via breastfeeding;
- Medication error;
- Occupational exposure.

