In the maintenance study (A3921096), both tofacitinib 5 mg BID and 10 mg BID demonstrated statistically significantly greater treatment effects versus placebo for remission at Week 52 (primary endpoint), mucosal healing at Week 52, and sustained corticosteroid free remission among subjects in remission at baseline (key secondary endpoints). Tofacitinib 5 mg BID and 10 mg BID also demonstrated statistically significantly higher proportions of subjects with clinical response compared with placebo. Time to treatment failure was statistically significantly different in the tofacitinib 5 mg BID and 10 mg BID treatment groups compared with placebo, with earlier and more frequent events in the placebo group. The efficacy of tofacitinib 5 mg BID and 10 mg BID was supported by all other secondary and exploratory efficacy endpoints and PROs.

The observed treatment effect was higher in the tofacitinib 10 mg BID group than the tofacitinib 5 mg BID group in the overall population for primary and key secondary endpoints, and was generally consistent across subgroups.

In the 52-week maintenance study, both the tofacitinib 5 mg BID and 10 mg BID doses appeared to be well tolerated. Most AEs were mild or moderate in severity, and the most frequent TEAEs were colitis ulcerative (higher incidence in the placebo group) and nasopharyngitis (higher incidence in the tofacitinib groups). Discontinuation from the study due to AEs occurred more frequently in the placebo group compared with the tofacitinib 5 mg BID and 10 mg BID groups, with the most frequent AE leading to discontinuation being colitis ulcerative (worsening of UC). Serious adverse event (SAEs) occurred at similar frequencies across treatment groups. More subjects in the tofacitinib treatment groups experienced infection AEs compared with placebo, though serious infections occurred at similar rates across treatment groups. The most frequent infection AE in all treatment groups was nasopharyngitis. There was a dose-dependent increase in the rate of herpes zoster (HZ).

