6.4. Subject Withdrawal

Should a subject withdraw from active treatment, the subject should complete the procedures listed at the Month 42/ET Visit. After completing the procedures for the ET visit, the subject should return for a safety evaluation to occur approximately 4 weeks after discontinuing investigational product as per the follow-up visit (see [Section 6.2.9](#)).

Subjects will be withdrawn from the study if any of the following occurs during the study treatment period:

- If rescue therapy is initiated or re-initiated for UC with the exception of oral 5-ASA or sulfasalazine.
- If a subject undergoes surgery for UC.

A subject may be withdrawn from the study for any of the safety concerns as listed in [Appendix 4](#).

If venous thromboembolism is confirmed, discontinue treatment with tofacitinib and withdraw the subject from the study ([Appendix 4](#)).

Subjects who develop a serious infection during the study, defined as any infection (viral, bacterial, and fungal) requiring hospitalization or parenteral antimicrobials or being classified as a serious adverse event should be withdrawn from the study (see [Section 7.3.4](#)).

All abnormal laboratory events of clinical significance should be followed until the laboratory values have returned to normal or baseline levels (see [Appendix 4](#)). Subjects who meet the discontinuation criteria described in [Appendix 4](#) will be withdrawn from the study.

Subjects who are withdrawn from this study will not be permitted to return to Study A3921139.

Withdrawal of consent:

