8. ADVERSE EVENT REPORTING

8.1. Requirements

The table below summarizes the requirements for recording safety events on the CRF and for reporting safety events on the Clinical Trial (CT) Serious Adverse Event (SAE) Report Form to Pfizer Safety. These requirements are delineated for 3 types of events: (1) SAEs; (2) non-serious adverse events (AEs); and (3) exposure to the investigational product under study during pregnancy or breastfeeding, and occupational exposure.

Safety Event	Recorded on the CRF	Reported on the CT SAE Report Form to Pfizer Safety Within 24 Hours of Awareness
SAE	All	All
Non-serious AE	All	None
Exposure to the investigational product under study during pregnancy or breastfeeding, and occupational exposure	All (regardless of whether associated with an AE), except occupational exposure	Exposure during pregnancy, exposure via breastfeeding, occupational exposure (regardless of whether associated with an AE)

All observed or volunteered events regardless of treatment group or suspected causal relationship to the investigational product(s) will be reported as described in the following paragraphs.

Events listed in the table above that require reporting to Pfizer Safety on the CT SAE Report Form within 24 hours of awareness of the event by the investigator **are to be reported regardless of whether the event is determined by the investigator to be related to an investigational product under study**. In particular, if the SAE is fatal or life-threatening, notification to Pfizer Safety must be made immediately, irrespective of the extent of available event information. This time frame also applies to additional new (follow-up) information on previously forwarded reports. In the rare situation that the investigator does not become immediately aware of the occurrence of an event, the investigator must report the event within 24 hours after learning of it and document the time of his/her first awareness of the event.

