8.1.2. Eliciting Adverse Event Information

The investigator is to record on the CRF all directly observed AEs and all AEs spontaneously reported by the study subject. In addition, each study subject will be questioned about the occurrence of AEs in a non-leading manner.

8.1.3. Withdrawal From the Study Due to Adverse Events (see also the [Subject Withdrawal](#) section)

Withdrawal due to AEs should be distinguished from withdrawal due to other causes, according to the definition of AE noted below, and recorded on the CRF.

When a subject withdraws from the study because of an SAE, the SAE must be recorded on the CRF and reported, as appropriate, on the CT SAE Report Form, in accordance with the [Requirements](#) section above.

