8.4. Special Situations

8.4.1. Protocol-Specified Serious Adverse Events

There are no protocol-specified SAEs in this study. All SAEs will be reported to Pfizer Safety by the investigator as described in previous sections, and will be handled as SAEs in the safety database.

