3.5. Safety Endpoints

The safety endpoints in this study include:

- Incidence and severity of adverse events (AEs).
- Incidence and severity of clinical laboratory abnormalities, and change from baseline in clinical laboratory values.
- Incidence of vital sign abnormalities and change from baseline in vital signs.

- Incidence of clinically significant changes in physical examinations from baseline.
- Safety events of interest including adjudicated safety events (eg, opportunistic infections, malignancy, gastrointestinal perforation, hepatic events, and cardiovascular events).

An adverse event is considered treatment emergent relative to a given treatment if the event starts after the first dose. The first dose is defined as the first dose in Study A3921288.

A 3-tier approach will be used to summarize AEs. Under this approach, AEs are classified into 1 of 3 tiers. Different analyses will be performed for different tiers (See [Section 6.6.1](#)).

Tier-1 events: These are pre-specified events of clinical importance and are maintained in a list in the product's Safety Review Plan.

Tier-2 events: These are events that are not tier-1 but are "common". A MedDRA Preferred Term is defined as a tier-2 event if there are at least 4 in any treatment group.

Tier-3 events: These are events that are neither tier-1 nor tier-2 events

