6.6. Safety Summaries and Analyses

The safety data will be summarized in accordance with Pfizer Data Standards.

All safety data will be summarized descriptively by dose group, regimen group and the subgroup of subjects who are initially assigned to tofacitinib 5 mg BID and later are retreated with tofacitinib 10 mg BID in the safety analysis set.

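### The overall AE, severe AE, SAE and AE-withdrawal totals include worsening UC, so they partly re-count lost efficacy as harm, and the SAP plans no version without it.

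*Protocol*

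**What the plan says.** Protocol 8.2.1 names "Progression/worsening of underlying disease" as an example of an AE. Collection is broad (Protocol 8.1): "All observed or volunteered events regardless of treatment group or suspected causal relationship to the investigational product(s) will be reported". There is no carve-out at the serious level either. Protocol 8.4.1 states "There are no protocol-specified SAEs in this study", so a UC event is an SAE whenever it meets a criterion in 8.2.3.

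On withdrawals, Protocol 8.1.3 says "Withdrawal due to AEs should be distinguished from withdrawal due to other causes, according to the definition of AE noted below". Protocol 6.4 lists this among the reasons for withdrawing a subject: "If rescue therapy is initiated or re-initiated for UC with the exception of oral 5-ASA or sulfasalazine".

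On the efficacy side, SAP 3.2 defines loss of remission as flare, using the four criteria in SAP 2.2.

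On the safety side, SAP 3.5 takes the incidence and severity of AEs as an endpoint. SAP 6.6 says "All safety data will be summarized descriptively by dose group, regimen group and the subgroup" of 5 mg subjects later re-treated with 10 mg. SAP 6.6.1 plans between-group estimates for tier-1 events (a pre-specified list) and tier-2 events (preferred terms with at least 4 in a group). It leaves the overall picture to a standard AE summary. Nothing in the SAP sets UC worsening apart in any total.

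**The concern.** Safety of the reduced dose is part of the primary objective. In a dose-reduction trial, the hoped-for benefit of 5 mg is better tolerability and the feared cost is more flares. If a flare counts in the efficacy analysis and again in the AE totals, those totals no longer answer the tolerability question on its own.

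The documents make this more than a theoretical worry. Protocol 1.2 reports that in the 52-week maintenance study worsening UC was among the most frequent treatment-emergent events and was more common on placebo. On withdrawals it adds: "with the most frequent AE leading to discontinuation being colitis ulcerative (worsening of UC". The same section reports a larger observed effect on 10 mg than on 5 mg. More UC events on 5 mg is therefore the direction to expect, and it works against 5 mg in any crude total. The overall rows are descriptive, but they are the rows a reader looks at first.

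**Working it through.** **1. The plan's own figure.** The only design figure is a 95% half-width of about 16 points for the Month 6 remission difference, with 65 per group and remission of 70% (Protocol 9.1). Check: 1.96 × √(2 × 0.70 × 0.30 / 65) = 0.158. It reproduces and is not in dispute.

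**2. Inputs for the illustration.** The documents give no expected AE rates, so every rate below is an assumption. The nearest figure is in Protocol 1.2: 72.7% still in remission 12 months after stepping down to 5 mg in the open-label study. The remaining 27.3% is not an AE rate, so it is not used.

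**3. Effect on any AE.** Take UC and non-UC events as independent, so P(any AE) = 1 − (1 − non-UC)(1 − UC). Assume non-UC AEs of 55% on 5 mg and 65% on 10 mg, a 10-point advantage for 5 mg.

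| UC AEs, 5 mg v 10 mg | Any AE, 5 mg | Any AE, 10 mg | Apparent advantage of 5 mg |
|---|---|---|---|
| 5% v 5% | 1 − 0.45 × 0.95 = 57.25% | 1 − 0.35 × 0.95 = 66.75% | 9.5 points |
| 10% v 5% | 1 − 0.45 × 0.90 = 59.5% | 66.75% | 7.25 points |
| 20% v 10% | 1 − 0.45 × 0.80 = 64.0% | 1 − 0.35 × 0.90 = 68.5% | 4.5 points |
| 30% v 15% | 1 − 0.45 × 0.70 = 68.5% | 1 − 0.35 × 0.85 = 70.25% | 1.75 points |

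**4. Effect on rarer totals.** Here the sign can change.
- SAEs: assume non-UC SAEs of 5% v 8% (3 points in favour of 5 mg) and UC SAEs of 10% v 5%. Then 1 − 0.95 × 0.90 = 14.5% and 1 − 0.92 × 0.95 = 12.6%, which is 1.9 points against 5 mg. UC SAE rates this high need UC events that meet a seriousness criterion, so this is a strong scenario.
- AE withdrawals: assume non-UC 3% v 6% and UC 10% v 5%. Then 1 − 0.97 × 0.90 = 12.7% and 1 − 0.94 × 0.95 = 10.7%, which is 2.0 points against 5 mg. If each subject has one withdrawal reason, the rates simply add: 13% v 11%, again 2 points.

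**5. Can the preferred-term table recover the non-UC total?** The UC term would probably appear in tier 2. With 65 on 5 mg, the chance of at least 4 cases is 0.41, 0.90 and 0.99 at assumed rates of 5%, 10% and 15%. But a subject with a UC event may have other AEs too, so the non-UC rate is known only to lie between (any AE − UC) and any AE. In the 20% v 10% row that is 44% to 64% on 5 mg and 58.5% to 68.5% on 10 mg. The difference (10 mg minus 5 mg) could then lie anywhere from 58.5 − 64 = −5.5 to 68.5 − 44 = +24.5 points, around an assumed truth of 10.

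**6. Set against sampling error.** At 64.0% v 68.5% with 65 per group, the 95% half-width is 1.96 × √(0.640 × 0.360 / 65 + 0.685 × 0.315 / 65) = 16.2 points. The shifts in step 3 lie inside it. They are a systematic displacement of the estimate and would not by themselves decide a conclusion.

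**The case against.** The case on the other side is substantial, and most of it narrows the point.

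- **The SAP specifies no formal comparison of the totals.** Its AE estimates with intervals are by tier, the tiered analysis is called exploratory, and no hypotheses are tested (SAP 5.1). The totals come through sponsor data standards whose layouts are not in the documents. This stands: the gap is in the SAP text, and the affected rows are descriptive.
- **Dose-related harms are examined event by event.** Herpes zoster is the harm for which the protocol reports a dose effect. Adjudicated events and special-interest incidence rates are also event-specific. A reader might infer that the whole safety comparison is compromised. The documents do not support that.
- **A UC withdrawal need not be coded as an AE withdrawal.** A reader might take Protocol 8.1.3 as settling it. Combined with 8.2.1 and the maintenance-study experience, it makes AE coding the expected route. But Protocol 6.4 lists UC rescue therapy and surgery apart from safety concerns, and the CRF is not available. If each withdrawal has one reason, a by-term withdrawal table could also be subtracted almost exactly.
- **The maintenance study does not show the effect between these doses.** Its contrast is placebo against active drug, and it reports similar SAE frequencies across groups. It shows how UC worsening was coded, and no more.
- **Worsening disease is a legitimate harm of a lower dose.** This stands, and it is why the non-UC count should not replace the all-AE count.
- **Post-escalation data.** A reader might add that dose-group data after escalation are dropped for 5 mg, while a 10 mg subject who flares and later withdraws is kept, so the dose-group withdrawal row could be distorted the other way. That follows from the SAP 5.3.3 cut, which removes every later AE and not only UC. It is a separate matter, and excluding UC terms would not fully repair it.

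What survives is that, for any AE and any SAE, overlapping preferred-term counts do not yield the non-UC total.

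**Conclusion.** The point holds for the overall rows only. The totals for any AE, severe AE, SAE and AE leading to withdrawal, by dose group and regimen group, partly re-count lost efficacy as harm, and the SAP plans no version that separates the two. The expected direction is to mask a tolerability gain on 5 mg. That is least certain for dose-group withdrawals, because of the post-escalation cut.

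The size cannot be stated from the documents. Under the assumed rates and independence, a 10-point any-AE advantage falls to between 9.5 and 1.75 points, and to 4.5 in the middle scenario. The SAE effect is limited to UC events that meet a seriousness criterion. A reader might conclude that recording worsening UC as an AE is itself an error. It is not: the definition and its reporting can stay as they are. This is a cheap improvement to a descriptive summary and does not undermine the planned event-specific analyses.

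**What to change.** In SAP 6.6 and 6.6.1, for the final analysis, present each overall row (any AE, severe AE, SAE, AE leading to withdrawal) twice, side by side, by dose group and regimen group. One row is the all-AE count as now. The other counts subjects with at least one event other than UC worsening. The second row is an addition and does not replace the first.

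Fix the term list in advance: the preferred term colitis ulcerative, plus terms for UC flare or for its symptoms when reported as a flare. The single preferred term alone would miss flares coded by symptom. Apply the list identically to both arms. Record the date of the change, because SAP 7.1 has the sponsor's study team unblinded from the Month 6 analysis onwards.

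In the disposition table, show withdrawals for UC worsening as their own category if the CRF does not already do so. Leave AE recording and SAE reporting unchanged.

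The cost is SAP wording and one extra footnoted row per overview table. The drawback is two versions of each total, which the footnote must explain. No new data are needed.

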8.2.2. Abnormal Test Findings

Abnormal objective test findings should be recorded as AEs when any of the following conditions are met:

- Test result is associated with accompanying symptoms; and/or
- Test result requires additional diagnostic testing or medical/surgical intervention; and/or
- Test result leads to a change in study dosing (outside of any protocol-specified dose adjustments) or discontinuation from the study, significant additional concomitant drug treatment, or other therapy; and/or
- Test result is considered to be an AE by the investigator or sponsor.

Merely repeating an abnormal test, in the absence of any of the above conditions, does not constitute an AE. Any abnormal test result that is determined to be an error does not require recording as an AE.

8.2.3. Serious Adverse Events

A serious adverse event is any untoward medical occurrence at any dose that:

- Results in death;
- Is life-threatening (immediate risk of death);
- Requires inpatient hospitalization or prolongation of existing hospitalization;
- Results in persistent or significant disability/incapacity (substantial disruption of the ability to conduct normal life functions);
- Results in congenital anomaly/birth defect.

Or that is considered to be:

- An important medical event.

Medical and scientific judgment is exercised in determining whether an event is an important medical event. An important medical event may not be immediately life-threatening and/or result in death or hospitalization. However, if it is determined that the event may jeopardize the subject or may require intervention to prevent one of the other AE outcomes, the important medical event should be reported as serious.

Examples of such events are intensive treatment in an emergency room or at home for allergic bronchospasm; blood dyscrasias or convulsions that do not result in hospitalization; or development of drug dependency or drug abuse.

8.2.4. Hospitalization

Hospitalization is defined as any initial admission (even less than 24 hours) in a hospital or equivalent healthcare facility, or any prolongation of an existing admission. Admission also includes transfer within the hospital to an acute/intensive care unit (eg, from the psychiatric wing to a medical floor, medical floor to a coronary care unit, or neurological floor to a tuberculosis unit). An emergency room visit does not necessarily constitute a hospitalization; however, the event leading to the emergency room visit is assessed for medical importance.

Hospitalization does not include the following:

- Rehabilitation facilities;
- Hospice facilities;
- Respite care (eg, caregiver relief);
- Skilled nursing facilities;

- Nursing homes;
- Same-day surgeries (as outpatient/same-day/ambulatory procedures).

Hospitalization or prolongation of hospitalization in the absence of a precipitating clinical AE is not in itself an SAE. Examples include:

- Admission for treatment of a preexisting condition not associated with the development of a new AE or with a worsening of the preexisting condition (eg, for workup of a persistent pretreatment laboratory abnormality);
- Social admission (eg, subject has no place to sleep);
- Administrative admission (eg, for yearly physical examination);
- Protocol-specified admission during a study (eg, for a procedure required by the study protocol);
- Optional admission not associated with a precipitating clinical AE (eg, for elective cosmetic surgery);
- Hospitalization for observation without a medical AE;
- Preplanned treatments or surgical procedures. These should be noted in the baseline documentation for the entire protocol and/or for the individual subject.

Diagnostic and therapeutic noninvasive and invasive procedures, such as surgery, should not be reported as SAEs. However, the medical condition for which the procedure was performed should be reported if it meets the definition of an SAE. For example, an acute appendicitis that begins during the reporting period should be reported if the SAE requirements are met, and the resulting appendectomy should be recorded as treatment of the AE.

